## 9.2 Exclusion Criteria

### 9.2.1 Subjects Transitioning from Pivotal Study 250901 or Pediatric Study 251101 (Cohort 1)

Subjects who have completed Baxter Pivotal Study 250901 or Pediatric Study 251101 and meet **ANY** of the following criteria are not eligible for this study:

- Subject received factor IX product(s) other than BAX326 upon completion of Baxter Pivotal Study 250901 or Pediatric Study 251101.
- Subject has been diagnosed with an acquired hemostatic defect other than hemophilia B.
- For subjects transferring from Pivotal Study 250901: The subject's weight is  $< 35$  kg or  $> 120$  kg.
- Subject's platelet count is  $< 100,000$ /mL.
- Subject has an abnormal renal function (serum creatinine  $> 1.5$  times the upper limit of normal).
- Subject has active hepatic disease with alanine aminotransferase (ALT) or aspartate aminotransferase (AST) levels  $\geq 5$  times the upper limit of normal.
- Subject is scheduled to receive during the course of the study, an immunomodulating drug (e.g. corticosteroid agents at a dose equivalent to hydrocortisone greater than 10 mg/day, or  $\alpha$ -interferon) other than anti-retroviral chemotherapy.
- Subject has a clinically significant medical, psychiatric, or cognitive illness, or recreational drug/alcohol use that, in the opinion of the investigator, would affect subject's safety or compliance.

- Subject is planned to take part in any other clinical study, with the exception of BAX326 Surgery Studyxvii as described in this protocol, during the course of the Continuation Study.
- Subject is a member of the team conducting this study or is in a dependent relationship with one of the study team members. Dependent relationships include close relatives (ie, children, partner/spouse, siblings, parents) as well as employees of the investigator or site personnel conducting the study.

### **9.2.2 Newly Recruited Subjects (Cohort 2)**

Newly recruited subjects who meet ANY of the following criteria are not eligible for this study:

- Subject has a history of FIX inhibitors with a titer  $\geq 0.6$  Bethesda Units (BU) (as determined by the Nijmegen modification of the Bethesda assay or the assay employed in the respective local laboratory) at any time prior to screening.
- Subject has a detectable FIX inhibitor at screening, with a titer  $\geq 0.6$  BU as determined by the Nijmegen modification of the Bethesda assay in the central laboratory.
- Subjects  $\geq 12$  years of age: Subject's weight is  $< 35$  kg or  $> 120$  kg
- Subject has a history of allergic reaction, eg, anaphylaxis, following exposure to FIX concentrate(s).
- Subject has a known hypersensitivity to hamster proteins or rFurin.
- Subject has evidence of an ongoing or recent thrombotic disease, fibrinolysis or disseminated intravascular coagulation (DIC).
- Subject has an abnormal renal function (serum creatinine  $> 1.5$  times the upper limit of normal).
- Subject has severe chronic liver disease as evidenced by, but not limited to, any of the following: International Normalized Ratio (INR)  $> 1.4$  hypoalbuminemia, portal vein hypertension including presence of otherwise unexplained splenomegaly and history of esophageal varices.
- Subject has active hepatic disease with alanine aminotransferase (ALT) or aspartate aminotransferase (AST) levels  $> 5$  times the upper limit of normal.

---

xvii Surgery Study 251002 was completed in May 2014. Thirty unique subjects underwent 38 surgeries.

- Subject has been diagnosed with an inherited or acquired hemostatic defect other than hemophilia B.
- Subject's platelet count is < 100,000/mL.
- Subject has a clinically significant medical, psychiatric, or cognitive illness, or recreational drug/alcohol use that, in the opinion of the investigator, would affect subject's safety or compliance.
- Subject is currently receiving, or is scheduled to receive during the course of the study, an immunomodulating drug (eg, corticosteroid agents at a dose equivalent to hydrocortisone greater than 10 mg/day, or  $\alpha$ -interferon) other than anti-retroviral chemotherapy.
- Subject has participated in another investigational study within 30 days of enrollment.
- Subject is a member of the team conducting this study or is in a dependent relationship with one of the study team members. Dependent relationships include close relatives (ie, children, partner/spouse, siblings, parents) as well as employees of the investigator or site personnel conducting the study.

### 9.3 Withdrawal and Discontinuation

Any subject may voluntarily withdraw (ie, reduce the degree of participation in the study) consent for continued participation and data collection. The reason for withdrawal will be recorded on the Completion/Termination eCRF. Assessments to be performed at the termination visit (including in cases of withdrawal or discontinuation) are described in Section 10.6 and Section 21.2. The data collected on withdrawn subjects will be used in the analysis and included in the clinical study report.

Discontinuation (ie, complete withdrawal from study participation) may be due to dropout (ie, active discontinuation by subject) or loss to follow-up (ie, discontinuation by subject without notice or action). Additionally, the investigator and sponsor have the discretion to discontinue any subject from the study if, in their judgment, continued participation would pose an unacceptable risk for the subject, or if the subject does not meet the eligibility criteria but was inadvertently enrolled in the study.

Subjects will also be discontinued from further study participation for the following reasons:

- The subject has developed an inhibitor to FIX  $\geq$  0.6 BU confirmed at the central laboratory.

- The subject with chronic hepatitis B or C has developed ALT/AST levels exceeding 5 times the upper limit of normal which may be confirmed by repeating the test.
- The subject has developed clinical signs of a thrombotic event.
- The subject has experienced severe allergic reaction(s), e.g. anaphylaxis, upon exposure to BAX326.
- The subject has received an immunomodulating drug (eg,  $\alpha$ -interferon, corticosteroid agents at a dose equivalent to hydrocortisone greater than 10 mg/day) other than anti-retroviral chemotherapy during the course of the study.
- The subject requires major surgery which will be performed outside the scope of the surgery study (e.g site not participating in surgery study, surgery study completedxviii)
- The subject becomes pregnant (if the subject is female of childbearing potential, which is not likely in this study). IP exposure will be discontinued. Attempts will be made to follow her through completion of the pregnancy. The investigator will record a narrative description of the course of the pregnancy and its outcome.
- The subject begins lactating (if the subject is female of childbearing potential, which is not likely in this study). IP exposure will be discontinued. The investigator will record a narrative description of the course of the baby's development.

Any subject who develops inhibitors or anaphylaxis, or demonstrates clinical signs of a thrombotic event, will be further followed up and treated according to best clinical practice.

---

xviii Surgery Study 251002 was completed in May 2014. Thirty unique subjects underwent 38 surgeries.

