## **10.6 Subject Completion/Discontinuation**

A subject is considered to have completed the study when he/she ceases active participation in the study because the subject has, or is presumed to have, followed the protocol. Reasons for completion/discontinuation will be reported on the Completion/Termination eCRF, including:

- Completed
- Eligibility criteria not met
- Screen failure
- AE
- Discontinuation by subject (eg, withdrawal of Informed Consent, lost to follow-up [defined as 3 documented unsuccessful attempts to contact the subject], dropout)
- Physician decision (e.g., pregnancy, progressive disease, non-compliance with IP/protocol violation(s), recovery)
- Study terminated by sponsor
- Any reason as specified in Section 9.3 “Withdrawal and Discontinuation”
- Or other (reason to be specified by the investigator, eg, technical problems)

Regardless of the reason, all data available for the subject up to the time of completion/discontinuation should be recorded on the appropriate eCRF. Refer to Section 9.3 for reasons for premature discontinuation or withdrawal.

Every effort will be made to have discontinued subjects complete the study completion/termination visit. Assessments to be performed at the termination visit (including in cases of withdrawal or discontinuation) can be found in Supplement [21.2](#) Schedule of Study Procedures and Assessments and Supplements [21.3](#) (Clinical Laboratory Assessments for Transition Subjects) and [21.4](#) (Clinical Laboratory Assessments for Newly Recruited Subjects). The reason for discontinuation will be recorded on the eCRF, and data collected up to the time of discontinuation will be used in the analysis and included in the clinical study report. All unused IP provided to the subject will be returned to the study site.

In the event of subject discontinuation due to an AE, clinical and/or laboratory investigations that are beyond the scope of the required study observations/assessments may be performed as part of the evaluation of the event. These investigations will take place under the direction of the investigator in consultation with the sponsor, and the details of the outcome may be reported to the appropriate regulatory authorities by the sponsor.

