#### 11.1.1 Determination of Incremental Recovery Over Time in Subjects Transitioning from BAX326 Pivotal or BAX326 Pediatric Study

FIX levels to determine IR will be assessed at the following visits:

- At screening
- Every 3 months  $\pm 1$  week
- At study termination/completion

Subjects will be infused with  $75 \pm 5$  IU/kg of BAX326. Upon completion of the infusion, the butterfly catheter should be flushed with at least 2 mL of saline solution. All assessments should be done at least 5 days after the previous dose of BAX326, and the subject must not actively bleed. The procedures for blood sampling are described in Section 11.1.6.

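### The termination-visit schedule sends discontinued subjects to a BAX326 recovery infusion, with no exception for those discontinued for a severe allergic reaction to BAX326

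*Protocol*

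**What the plan says.** Protocol 9.3 lists mandatory reasons for discontinuation. One reads "The subject has experienced severe allergic reaction(s), e.g. anaphylaxis, upon exposure to BAX326". A confirmed FIX inhibitor of 0.6 BU or more and signs of thrombosis are also on the list.

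For what happens next, 9.3 states "Assessments to be performed at the termination visit (including in cases of withdrawal or discontinuation) are described in Section 10.6 and Section 21.2". Section 10.6 adds "Every effort will be made to have discontinued subjects complete the study completion/termination visit" and gives the content of the visit: "Assessments to be performed at the termination visit (including in cases of withdrawal or discontinuation) can be found in Supplement" 21.2, with the laboratory work in 21.3 and 21.4.

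Those supplements include recovery at the termination visit. Section 11.1.1 introduces its list for transitioning subjects with "FIX levels to determine IR will be assessed at the following visits", and the list ends with study termination or completion. Section 11.1.3 does the same for newly recruited and PK-tailored subjects. Table 21.1-1 item 8 spells the step out: a pre-infusion sample, an infusion of 75 ± 5 IU/kg, then a sample at 30 minutes.

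On care after these events, 9.3 says "Any subject who develops inhibitors or anaphylaxis, or demonstrates clinical signs of a thrombotic event, will be further followed up and treated", with best practice as the standard. For pregnancy and for lactation it is more definite: "IP exposure will be discontinued".

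**The concern.** A subject who has just had a severe allergic reaction to BAX326 is taken off the study for that reason. The schedule for the closing visit then calls for one more full dose of the same product, for measurement only. Section 12.7.2 says that such reactions can progress to life-threatening anaphylaxis. Section 9.2.2 keeps out new subjects with a past allergic reaction to any FIX concentrate.

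An avoidable re-exposure is at stake. The primary analysis is not affected. A site that follows the tables literally gives the infusion. A site that does the safe thing departs from the written schedule and must justify it under a general clause.

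**Working it through.** **1. The route from discontinuation to infusion**

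- 9.3: discontinue for severe allergic reaction to BAX326; termination-visit assessments apply on discontinuation; see 10.6 and 21.2.
- 10.6: try to have discontinued subjects attend; see 21.2, 21.3 and 21.4.
- Tables 21.2-1 and 21.2-2, row for incremental recovery: marked at termination, no qualifier.
- Tables 21.3-1 and 21.4-1, row for FIX recovery: marked at termination. Footnote b asks for wash-out and says nothing of the reason for stopping.
- 11.1.1 and Table 21.1-1 item 8: dose 75 ± 5 IU/kg, so 70 to 80 IU/kg.
- Table 11.1-3 (newly recruited and PK-tailored subjects): the PK-tailored dose if higher. Section 8.1.3 caps that dose at 120 IU/kg. Item 8 gives only 75 ± 5, so the two places differ on the dose.

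There is no separate early-termination column or visit.

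**2. Search for an exception**

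- 9.3 follow-up clause: covers follow-up and treatment. It names inhibitors, anaphylaxis and thrombosis, but neither the recovery infusion nor stopping the product.
- 12.7.2 (after an allergic reaction) and 12.7.1.2 (after an inhibitor): add blood tests and waive nothing.
- 12.2 (urgent safety measures) and 16.5 (deviation for immediate hazard): permit withholding, with notice to the sponsor.
- Item 8: its only preconditions are wash-out and no active bleeding.
- SAP: no exception.

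The only explicit stops of product in the 9.3 list are those for pregnancy and lactation.

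**3. How many subjects could be affected**

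Inputs: 6.5 reports no severe allergic reactions, inhibitors or thrombotic events in 99 subjects, with a cut-off of 14 June 2013. The number of new subjects is taken as 25 (the protocol says approximately or at least 25). They are not among the 99, because Amendment 4, which added them, is dated 31 July 2013. No figure is given for Cohort 1: 82 of the 99 were already in this study, and the number remaining is not stated.

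- One-sided 95% upper bound for 0/99, per event type: 1 − 0.05^(1/99) = 0.0298.
- Expected cases in 25 at that bound: 25 × 0.0298 = 0.745.
- Chance of at least one case at that bound: 1 − (1 − 0.0298)^25 = 0.531.

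The protocol also gives lower benchmarks:

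- 6.5 expects a risk profile like that of BeneFIX and lists allergic reactions, including anaphylaxis, as rare (1/10,000 to 1/1,000). Read per subject, which is an assumption because the denominator is not stated, 25 subjects give 25 × 0.0001 = 0.0025 to 25 × 0.001 = 0.025 expected cases.
- 6.1 cites a surveillance study in which 2 of 244 subjects developed inhibitors and anaphylaxis: 2/244 = 0.0082, so 25 × 0.0082 = 0.2 expected, and 1 − (1 − 0.0082)^25 = 0.19.

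All of these count events. An unsafe infusion also needs the subject to attend and the site to infuse anyway. The documents give no probability for either, so the event figures are ceilings.

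**The case against.** The strongest reply is that nobody would give this infusion, and that the protocol already points away from it. Discontinued subjects leave the study and return unused product. The 9.3 clause says that those with inhibitors, anaphylaxis or thrombosis "will be further followed up and treated according to best clinical practice". Sections 12.2 and 16.5 allow immediate protective action. Anaphylaxis is a serious adverse event, reportable to the sponsor within 24 hours, and item 8 needs at least 5 days of wash-out, so the sponsor would normally know first. The opening of item 8 and the termination-column footnotes describe completers (100 exposure days or licensure), and 10.6 asks for best effort only.

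Much of this stands. It makes an actual infusion unlikely. It does not remove the conflict, because 9.3 and 10.6 expressly carry the termination schedule over to discontinued subjects, and permission to withhold is not a waiver. Reading the follow-up clause as deliberately leaving out severe reactions short of anaphylaxis would be over-literal, since 9.3 and 12.7.2 treat the two together. The point does not depend on that reading.

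A reader might go further and infer that all three reasons call for an automatic waiver. The documents do not support that. Section 6.2 does warn of anaphylaxis on re-exposure when inhibitors appear, but it also describes immune tolerance induction with large FIX doses. SAP 5.5 wants end-of-study recovery in order to see whether antibodies have affected it. For thrombosis the support is thinner still: 9.2.2 bars new subjects with ongoing or recent thrombotic disease.

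**Conclusion.** The concern holds for severe allergic reaction: as written, the schedule includes an elective re-exposure that no clause waives. Probability is low and severity high, so it should be fixed, but it does not call the trial or its analysis into question.

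The size rests on 25 new subjects with the same risk as the 99 already reported. On that basis the ceiling is about 0.75 expected severe allergic reactions, and the BeneFIX benchmark puts the count far lower. A reader might take the 53% as the chance of an unsafe infusion. It is the chance of at least one event if the true rate sits at the upper confidence bound, before any allowance for attendance or clinical judgement. Nor does the text amount to a deliberate instruction to rechallenge; it is a cross-reference that was not limited by reason for stopping.

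**What to change.** Add to 10.6, and as a footnote to the termination-visit recovery rows of Tables 21.2-1, 21.2-2, 21.3-1 and 21.4-1, a rule to this effect: *The recovery infusion and post-infusion samples are omitted in subjects discontinued for severe allergic reaction or anaphylaxis. In subjects discontinued for a thrombotic event or a confirmed FIX inhibitor they are omitted unless the investigator, in agreement with the sponsor, judges the infusion safe. All assessments that do not need the infusion are still done.*

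The drafting cost is one rule in 10.6 and one footnote in four tables. The analytic cost is a few missing end-of-study recovery values. Some may come from inhibitor subjects, in whom SAP 5.5 most wants the comparison with baseline. The report should state how many values were omitted and why, and show these subjects' earlier 3-monthly recoveries in the by-subject listing of SAP 9.1. Those earlier values may predate the inhibitor, so they replace the lost comparison only in part.

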## **10. STUDY PROCEDURES**

### **10.1 Informed Consent and Enrollment**

Any patient who provides informed consent (ie, signs and dates the informed consent form and assent form, if applicable) is considered enrolled in the study.

### **10.2 Subject Identification Code**

The following series of numbers will comprise the Subject Identification Code (SIC): protocol number (ie, 251001) to be provided by the sponsor, 2-digit number study site number (e.g., 02) to be provided by the sponsor, and 4-digit subject number (e.g., 0003) reflecting the order of enrollment (ie, signing the informed consent form). For example, the third subject who signed an informed consent form at study site 02 will be identified as Subject 251001-020003. All study documents (e.g., CRFs, clinical documentation, sample containers, drug accountability logs, etc.) will be identified with the SIC. Additionally, a uniquely coded SIC(s) is permitted as long as it does not contain a combination of information that allows identification of a subject (e.g., collection of a subject's initials and birthdate would not be permitted), in compliance with laws governing data privacy.

### **10.3 Screening and Study Visits**

The study site is responsible for maintaining an enrollment/screening log that includes all subjects enrolled. The log will also serve to document the reason for a screening failure.

A detailed breakdown of the study procedures is shown in Supplement [21.1](#) “Flow Diagram of Study Procedures”. Details on the procedures and assessments to be performed at each study visit, including screening, can be found in Supplement [21.1](#) “Schedule of Study Procedures and Assessments” and Supplements [21.3](#) “Clinical Laboratory Assessments for Transition Subjects” and [21.4](#) “Clinical Laboratory Assessments for Newly Recruited Subjects”.

Blood sampling and laboratory analyses can be repeated if the primary sample has been lost or damaged. All screening data will be collected and reported in eCRFs, regardless of screening outcome. For the purpose of analysis, only the data from the latest retest will be used.

Subjects should not be actively bleeding at the time of screening and at the scheduled study visits.

The following provisions apply for subjects who are enrolled in parallel in the BAX326 Surgery Study (Protocol 251002)xix:

Once a subject has signed informed consent for the BAX326 surgery study, s/he continues receiving treatment with IP as part of this BAX326 continuation study until the start of surgery. If a regular study visit has taken place within 4 weeks of the screening visit for the surgery study, the safety laboratory data from the current study can be used. Similarly, if a regular study visit is planned for this study, and the surgery study's completion/termination visit falls within a  $\pm$  2-week window of this visit, then the results from this study will be used for the completion/termination visit of the surgery study.

#### **10.3.1 Subjects Transitioning from BAX326 Pivotal or BAX326 Pediatric Study (Cohort 1)**

The screening visit will be performed on the same day as the completion/ termination visit for the 250901 (pivotal) or 251101 (pediatric) protocol.xx The Informed Consent will be obtained before any procedures related to the BAX326 Continuation study are performed. Tests performed for the BAX326 completion/ termination visit of the main study will not be repeated for screening in Study 251001, and the relevant data obtained for the 250901 or 251101 completion/termination visit will be transcribed to the screening visit eCRF.

Following the screening visit, subjects will continue receiving BAX326 until his/her eligibility for the study is confirmed. If the eligibility criteria are not met, a completion/termination visit will be performed at the Week 4 $\pm$ 1 visit following screening.

#### **10.3.2 Newly Recruited Subjects (Cohort 2)**

All screening/baseline evaluations must be completed within 42 days or repeated if more than 42 days have elapsed. Exemptions may be granted for administrative reasons by the sponsor, eg, delay in availability of laboratory results. For the purpose of analysis, only the data from the most recent screening visit will be used. If a subject does not satisfy all screening criteria, the same subject may be re-screened at a later date. A complete or partial re-screen may also become necessary at the discretion of the investigator or sponsor. All screening data will be collected and reported in eCRFs, regardless of screening outcome.

---

xix Surgery Study 251002 was completed in May 2014. Thirty unique subjects underwent 38 surgeries.

xx Pivotal Study 250901 and Pediatric Study 251101 have been completed (Last Subject Out: 03 May 2012 [Pivotal] and 14 May 2013 [Pediatric]).

Subjects should not be actively bleeding at the time of screening and at the scheduled study visits, and a wash-out period of at least 5 days, preferably 7 days, should be observed.

